5.5 General Considerations

Unless otherwise stated, all hypotheses will be tested at a 2-sided significance level of 0.05 and 95% confidence interval. All continuous measurements will be summarised descriptively at each visit by treatment using observed data.

Summary of continuous variables will be presented using N, Mean, Standard Error of mean (SE), Standard Deviation (SD), Median and Range (Minimum and Maximum). The categorical variables will be presented using number and percentage based on N.

For measurements over time mean values will be plotted to explore the trajectory over time. LOCF imputed data will be used as the basis for plotting data along with bars as standard error (SE) or Standard Deviation (SD), if not otherwise specified.

Primary endpoints of incidence of COVID-19 symptoms and Hospitalizations due to COVID-19 symptoms will be analysed based on binomial model and p-value will be displayed using two-sample binomial proportion test.

Additionally, time to first incidence of COVID-19 symptoms will analysed using Kaplan-Meir method.

A standard analysis of covariance (ANCOVA) model will be applied for secondary endpoints followed by Tukey's multiple comparison test to test the the significance of the effects of the treatment. The model includes treatment as fixed factor and the corresponding baseline value as a covariate.

Tukey's multiple comparison tests will be tested as two-sided hypotheses at a 5% level of significance. Treatment differences will be confirmed and considered significant if p-value reported is < 0.05 .

Protocol Number: HBCOVID02
Hope Biosciences
Statistical Analysis Plan

Confidential

Date: 14-Oct-2021
Version: 1.0
Status: Final

Presentation of results from a statistical analysis will include the estimated mean treatment effects (Least Square Means (LSMeans)) for absolute values and change from baseline. For all endpoints analysed statistically, estimated mean treatment differences will be presented together with two-sided 95% confidence intervals and p-values obtained using Tukey's method, and results from following paired comparisons will be displayed,

1. HB-adMSCs 200MM vs Placebo
2. HB-adMSCs 100MM vs Placebo
3. HB-adMSCs 50MM vs Placebo

All safety evaluations will be presented using Safety Analysis Set. The efficacy analysis will be presented using Efficacy analysis set.

Individual safety and efficacy parameters will be listed.

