5.4 Multiple Comparisons and Multiplicity

The primary comparison of interest is the overall comparison between HB-adMSCs treatments and Placebo for the primary endpoint, incidence of the hospitalizations due to COVID-19 symptoms and incidence of the COVID-19 symptoms, so multiplicity adjustment is not needed. However, for exploratory purposes we perform a pair-wise comparison will done and results from following paired comparisons will be displayed to find the paired wise differences,

1. HB-adMSCs 200MM vs Placebo
2. HB-adMSCs 100MM vs Placebo
3. HB-adMSCs 50MM vs Placebo

We do statistical analysis for the primary endpoints and secondary outcomes as exploratory and test the outcome using $\alpha = 0.05$.

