7.2. Secondary Efficacy Analyses

7.2.1. Endpoints / Variables

Change from baseline to the end of study period, Week 26 in,

- Leukocyte differential counts
- C-Reactive Protein
- TNF-alpha
- IL-6
- L-10
- SF-36 questionnaire score

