7.2.4.1. Statistical Methodology Specification

Change from baseline to Week 26 of treatment:

The secondary endpoint analysis is the overall treatment comparison between HB-adMSCs treatments and placebo. A pair-wise comparison of HB-adMSCs 200MM vs Placebo, HB-adMSCs 100MM vs Placebo and HB-adMSCs 50MM vs Placebo are also described in this table.

Secondary endpoint will be analysed using the standard ANCOVA model followed by Tukey's multiple comparison test to test the the significance of the effects of the treatment. The model includes treatment as fixed factor and the baseline value as a covariate.

Change from baseline to Week 14 end of infusion treatment:

The secondary endpoint analysis is the overall treatment comparison between HB-adMSCs treatments and placebo after Week 14 of infusion. A pair-wise comparison of HB-adMSCs 200MM vs Placebo, HB-adMSCs 100MM vs Placebo and HB-adMSCs 50MM vs Placebo are also described in this table.

Secondary endpoint will be analysed using the standard ANCOVA model followed by Tukey's multiple comparison test to test the the significance of the effects of the

Protocol Number: HBCOVID02
Hope Biosciences
Statistical Analysis Plan

Confidential

Date: 14-Oct-2021
Version: 1.0
Status: Final

treatment. The model includes treatment as fixed factor and the baseline value as a covariate.

Sensitivity/supportive analysis model

Change from baseline values of treatment will be analysed using the standard ANCOVA model based on efficacy analysis set followed by Tukey's multiple comparison test to test the the significance of the effects of the treatment. The model includes treatment as fixed factor and the baseline value as a covariate. A pair-wise comparison of HB-adMSCs 200MM vs Placebo, HB-adMSCs 100MM vs Placebo and HB-adMSCs 50MM vs Placebo are also described in this table for secundar endpoints.

A repeated measurements analysis (RMA) of value and change from baseline over Week 26 of treatment will be performed on the efficacy analysis sets, followed by Tukey's multiple comparison test to test the the significance of the effects of the treatment.

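### SAP 5.5 treats secondary differences as confirmed at p < 0.05 while 5.4 calls the same outcomes exploratory, so a chance finding could be reported as confirmed

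*SAP*

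**What the plan says.** SAP 5.4 (Multiple Comparisons and Multiplicity) gives the status of the tests: "We do statistical analysis for the primary endpoints and secondary outcomes as exploratory and test the outcome using" a 5% alpha. It also says of the primary comparison, "so multiplicity adjustment is not needed"; the reason offered is that a single overall comparison is of interest, which does not concern the secondary endpoints.

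SAP 5.5 (General Considerations) describes the secondary analysis: an ANCOVA "model will be applied for secondary endpoints followed by Tukey's multiple comparison test". It fixes the level, "Tukey's multiple comparison tests will be tested as two-sided hypotheses at a 5% level of significance", and follows at once with the decision rule: "Treatment differences will be confirmed and considered significant if p-value reported is" below 0.05. The contrasts to be displayed are each of the three doses against placebo.

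SAP 7.2.1 lists six secondary variables: "Leukocyte differential counts", CRP, TNF-alpha, IL-6, IL-10 and an SF-36 score. SAP 7.2.4.1 analyses change from baseline to Week 26 and also "Change from baseline to Week 14 end of infusion treatment". The protocol's schedule of assessments (Table 2) collects all six at both visits.

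**The concern.** A difference that 5.4 makes exploratory becomes confirmed under 5.5 once its p-value is below 0.05. A confirmatory label needs error control over the set of tests from which a positive result may be picked. Here the control stops at the edge of one endpoint at one visit; no hierarchy, gatekeeping or adjusted alpha spans endpoints or visits.

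The label matters because these markers carry part of the efficacy case. The protocol synopsis names the blood count with differential as the means of evaluating efficacy. The protocol's alternative hypothesis for efficacy covers primary and secondary endpoints alike. A marker difference reported as confirmed could be read as support for that hypothesis.

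**Working it through.** **Inputs.** From the documents: two-sided alpha 0.05 (SAP 5.5); four arms, hence 4 × 3 / 2 = 6 Tukey pairs, of which 3 are displayed (SAP 5.5); 6 endpoints (SAP 7.2.1); 2 visits (SAP 7.2.4.1); at most 53 patients (protocol, Determination of Sample Size); 15% drop-out (protocol synopsis). Assumptions: arms of 14, 13, 13 and 13, since the documents give no usable per-arm sizes for 53 patients; normal data; no true effect in any arm. A family below means one endpoint at one visit.

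**Step 1: reproduce the plan's 5% within one family.** Residual degrees of freedom for the ANCOVA are 53 − 4 − 1 = 48. The 5% studentized-range critical value for four groups is 3.764, or 3.764 / √2 = 2.661 on the t scale. In 400,000 simulated null trials, at least one of the six pairs passed this limit in 4.99%. With 45 patients (53 × 0.85 = 45.05) the figure was 5.05%. Tukey therefore does what 5.5 says within a family.

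The three displayed contrasts are half of the six pairs, so their joint error rate is lower: 2.8% with 53 patients and 2.9% with 45.

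**Step 2: several families, independent.** The chance of at least one false positive in k families at rate a is 1 − (1 − a)^k.

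| Families | k | Displayed contrasts, a = 0.028 | All six pairs, a = 0.05 |
|---|---|---|---|
| Six endpoints, one visit | 6 | 1 − 0.972^6 = 16% | 1 − 0.95^6 = 26% |
| Six endpoints, both visits | 12 | 1 − 0.972^12 = 29% | 1 − 0.95^12 = 46% |
| Components split (assumption), both visits | 34 | 1 − 0.972^34 = 62% | 1 − 0.95^34 = 83% |

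The last row assumes 5 leukocyte types, 4 markers and 8 SF-36 scales: (5 + 4 + 8) × 2 = 34. The protocol describes eight SF-36 scales, but the SAP lists one score. The number of cell types is in neither document.

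**Step 3: correlated families.** Endpoints and visits come from the same patients, so independence is the upper case. Simulating a common correlation of 0.5 between all families gives:

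| k | Displayed contrasts | All six pairs |
|---|---|---|
| 6 | 13% | 21% to 22% |
| 12 | 21% to 22% | 33% to 34% |
| 34 | 40% | 56% to 57% |

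The ranges reflect simulation error. The value 0.5 is illustrative; the documents give no correlations.

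**Not counted.** SAP 7.2.4.1 also names an overall comparison of the cell-treated groups with placebo, a repeated-measures analysis and a linear mixed model. These are further looks at the same endpoints.

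**The case against.** The best reply is that confirmed is loose wording. The sentence comes straight after the Tukey 5% level and may mean only that a result is declared statistically significant. The SAP's English is rough elsewhere, and 5.4, the section devoted to multiplicity, already states exploratory status. This reading is possible, and it limits how serious the point is. It does not remove it, because the SAP never says that 5.4 overrides 5.5, and the 5.5 sentence is the one that tells the analyst what to conclude from a p-value. If the loose reading is the intended one, correcting the sentence costs nothing.

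It is also fair that Tukey already protects the dose comparisons within each endpoint. Step 1 confirms this, and the lower rate for the displayed contrasts is used throughout.

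A reader might infer more than the documents support:

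- *That a false confirmed result is likely.* On the endpoints as listed, every figure is below one half. For the displayed contrasts, one half is passed only with both composites split, both visits counted and weak correlation: with 34 families, 62% if independent, about 52% at a correlation of 0.3 and 40% at 0.5. The SAP does not state those splits.
- *That the 83% figure describes what will be reported.* It needs the same splits, and it counts dose-versus-dose pairs that are not among the comparisons 5.5 says will be displayed.
- *That primary events will be rare and the markers will lead the report.* The documents give no expected event rate and do not say which results will be emphasised.

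**Conclusion.** The contradiction between 5.4 and 5.5 is real. Followed as written, 5.5 would allow a confirmatory conclusion from testing that is uncontrolled across endpoints and visits, so a chance finding could be reported as confirmed. The figures to rely on are those for the six endpoints as listed over both visits: 29% for the displayed contrasts and 46% for all pairs as independent upper cases, and about 21% to 22% and 33% to 34% at a correlation of 0.5. They assume no true effect, normal data and near-equal arms; the per-family rates barely change between 53 and 45 patients. The 34-family figures are a labelled worst case only. This should be corrected. It changes what the trial may claim, not how any endpoint is analysed.

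**What to change.** In SAP 5.5, replace the rule that treatment differences are confirmed and considered significant with: *p < 0.05 is nominal; secondary results are exploratory (section 5.4) and no confirmatory claim will be made.* Stating the number of secondary tests beside the results would help the reader but is optional.

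The cost is one sentence. No data, alpha or model changes; secondary claims become less favourable. If the sponsor did want a confirmatory secondary claim, the rewording would not be enough and control across the family would be needed. Bonferroni over 12 families, for illustration, would use 0.05 / 12 = 0.0042 for each.

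The change covers secondary results only. SAP 5.4 also calls the primary endpoints exploratory, while 2.3 sets formal 5% hypotheses for them; that has to be reconciled separately.

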5. CONSIDERATIONS FOR DATA ANALYSES AND DATA HANDLING CONVENTIONS

5.1 Study Treatment & Sub-group Display Descriptors

Treatment Group Descriptions		
Protocol treatment arm	Data Displays for Reporting	
Treatment Arm	Treatment Arm	Order in TLF
Arm 1 (allogeneic HB-adMSCs 200MM)	aHB-adMSCs 200MM	1
Arm 2 (allogeneic HB-adMSCs 100MM)	aHB-adMSCs 100MM	2
Arm 3 (allogeneic HB-adMSCs 50MM)	aHB-adMSCs 50MM	3
Arm 4 (Placebo)	Placebo	4

Treatment comparisons will be displayed as follows using the descriptors as specified in the statistical analysis:

1. HB-adMSCs 200MM vs Placebo
2. HB-adMSCs 100MM vs Placebo
3. HB-adMSCs 50MM vs Placebo

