6. STUDY POPULATION ANALYSES

6.1. Overview of Planned Study Population Analyses

The study population analyses will be based on the Safety analysis set.

Study population analyses including analyses of subject disposition, demographic and baseline characteristics, medical history, prior and concomitant medications. Additionally, including tobacco usage and alcoholic abuse.

A two sample binomial test will be applied for primary endpoints to calculate p-value comparing binomial proportions for incidence of COVID-19 symptoms and Hospitalizations due to COVID-19 symptoms.

p-value for treatment difference using one-way Analysis of variance (ANOVA) is displayed for baseline characteristics. A standard analysis of covariance (ANCOVA) model will be applied for secondary endpoints followed by Tukey's multiple comparison test to test the the significance of the effects of the treatment. The model includes treatment as fixed factor.

Details of the planned displays are presented in Appendix 5: List of Data Displays.

Categorical variables will be summarized by the number and percentage of subjects, and the continuous parameters will be summarized by n, mean, standard error of mean, median, sample standard deviation, minimum and maximum unless otherwise specified.

Disposition summary includes, subject screened, randomized and disposition at end of study – Week 26 along with reasons for withdrawals will be presented based on number of subjects and percentage. Subjects in different analysis populations also will be presented.

Protocol Number: HBCOVID02
Hope Biosciences
Statistical Analysis Plan

Confidential

Date: 14-Oct-2021
Version: 1.0
Status: Final

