7.2.2. Summary Measures

Least square mean (LSM) and LSM mean difference between treatments.

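### Secondary endpoints: Tukey's method protects six pairs, but the SAP text lists only three dose-versus-placebo comparisons, so intervals are about 10% wider than Dunnett's (minor efficiency point)

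*SAP*

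**What the plan says.** SAP 2.2 sets out four groups: 200MM, 100MM, 50MM and placebo. For the secondary endpoints, SAP 7.2.4.1 states: "Secondary endpoint will be analysed using the standard ANCOVA model followed by Tukey's multiple comparison test". The model has treatment as a fixed factor and the baseline value as a covariate, and it is applied at Week 14 and at Week 26. SAP 6.1 repeats the method ("A standard analysis of covariance (ANCOVA) model will be applied for secondary endpoints followed by Tukey's multiple comparison test"). SAP 5.5 carries it into the reported results: "estimated mean treatment differences will be presented together with two-sided 95% confidence intervals and p-values obtained using Tukey's method". The supportive analyses use Tukey too. In 7.2.4.1, "A repeated measurements analysis (RMA) of value and change from baseline over Week 26 of treatment will be performed on the efficacy analysis sets", again followed by Tukey's test.

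The comparisons to be shown are the same three throughout. SAP 5.1 introduces them with "Treatment comparisons will be displayed as follows using the descriptors as specified in the statistical analysis", SAP 5.5 lists them after naming Tukey's method, and SAP 7.2.4.1 says: "A pair-wise comparison of HB-adMSCs 200MM vs Placebo, HB-adMSCs 100MM vs Placebo and HB-adMSCs 50MM vs Placebo are also described in this table". No section available for this review lists a dose-versus-dose comparison. SAP 5.4 describes the analyses of the primary endpoints and secondary outcomes as exploratory, at a level of 0.05.

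**The concern.** Four arms form six pairs: three of dose against placebo and three of dose against dose. Tukey's critical value is set so that the chance of any false rejection among all six is 5%. If only the three placebo comparisons are reported, part of that protection is spent on contrasts that nobody will see. Dunnett's method holds 5% for exactly the family of each dose against a shared control, with a smaller critical value.

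At stake is precision. With about 11 to 13 subjects per arm the intervals are wide under either method. The Protocol (Determination of Sample Size) caps the trial at 53, so the lost width cannot be recovered by enrolling more subjects.

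**Working it through.** The documents give no critical value, interval width or power for these comparisons, so there is no planned figure to reproduce first.

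**Inputs from the documents**
- Four arms; three listed comparisons (SAP 2.2, 5.1, 5.5, 7.2.4.1).
- Two-sided 5% level (SAP 5.5).
- ANCOVA with treatment and baseline, so residual df = N − 4 − 1 = N − 5.
- N = 53 (SAP 2.2; Protocol, Determination of Sample Size). The Protocol synopsis assumes 15% drop-out: 53 × 0.85 = 45.05, so about 45 completers.

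**Assumptions**
- The documents give only 3:1 active to placebo and do not state the split among doses. I take near-equal arms: 13/13/13 and placebo 14 at N=53, and 11.25 per arm at N=45.
- Differences are in units of the residual SD after ANCOVA. The effect sizes are illustrative, since the documents give none.

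**Critical values**
- Tukey: c = q(0.95; 4 groups, df)/√2.
- Dunnett: the c that solves P(max |Tᵢ| ≤ c) = 0.95 for three t statistics sharing one control, with correlation nᵢ/(nᵢ + n₀). Here that is 13/27 = 0.48 at N=53 and 0.5 with equal arms.

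| | df | Tukey | Dunnett | Ratio |
|---|---|---|---|---|
| N=53 (13/13/13/14) | 48 | 2.661 | 2.429 | 1.096 |
| N=45 (equal arms) | 40 | 2.680 | 2.441 | 1.098 |

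The ratio of interval widths is the ratio of critical values, so it depends on no assumed effect or SD. Squared, it is 1.096² = 1.20: equal width under Tukey would need about 20% more subjects.

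**Half-width at N=53.** The standard error factor is √(1/13 + 1/14) = 0.385. Tukey: 2.661 × 0.385 = 1.025 SD. Dunnett: 2.429 × 0.385 = 0.936 SD. The saving is 0.09 SD.

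**Actual error of Tukey over the three pairs.** P(max |Tᵢ| > 2.661) = 0.0285 at N=53, and 0.0284 at N=45 with its own critical value of 2.680.

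**Power per comparison** (noncentral t; noncentrality = difference ÷ standard error factor)

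| Difference (SD) | N=53 Tukey | N=53 Dunnett | N=45 Tukey | N=45 Dunnett |
|---|---|---|---|---|
| 0.5 | 10% | 14% | 8% | 12% |
| 0.8 | 29% | 37% | 23% | 30% |
| 1.0 | 48% | 57% | 39% | 48% |
| 1.2 | 67% | 75% | 57% | 66% |

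**Sensitivity to the split at N=53.** With 10/10/10/23 the ratio is 1.084; with 14/14/14/11 it is 1.103. Reading 3:1 as 3:3:3:1 (16/16/16/5) gives 1.136, but the Protocol and SAP 2.2 set 3:1 between HB-adMSCs and placebo as a whole, so that reading is strained.

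**Error across endpoints.** SAP 7.2.1 names six variables. At Weeks 14 and 26 they make 12 families, counting the leukocyte differential and the SF-36 once each. With no true effect and independent families, the chance of at least one false positive is 1 − (1 − 0.0285)¹² = 29% with Tukey and 1 − 0.95¹² = 46% with Dunnett. Under perfect dependence these fall to 2.8% and 5%.

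**The case against.** **Tukey is a valid, pre-specified method, and choosing Dunnett is a preference.** The first half stands. Tukey keeps the familywise error below 5%, so no false claim follows from it. A reader might infer from the mismatch that the analysis is wrong; the documents do not support that. What remains is that Dunnett serves the listed comparisons better at almost no cost.

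**Dose-versus-dose pairs may be wanted.** A list of displayed comparisons does not prove that other pairs are of no interest. SAP 7.2.2 words the summary measure generally: "Least square mean (LSM) and LSM mean difference between treatments". Appendix 5, which lists the data displays, was not available for this review. This stands as a condition on the fix: if Appendix 5 plans dose-versus-dose displays, Tukey is a reasonable choice.

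**Tukey's conservatism is useful when many endpoints are tested.** The cost is real (29% against 46% above). It would be larger if the eight SF-36 scales described in the Protocol were tested separately: 2 × (5 + 8) = 26 families, giving 53% and 74% under independence. But the SAP does not offer Tukey as control across endpoints, and it does not provide it. The cost belongs in the decision and does not defeat the change.

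**A stronger reading concerns the lead comparison.** SAP 7.2.4.1 states: "The secondary endpoint analysis is the overall treatment comparison between HB-adMSCs treatments and placebo". A reader might infer that the lead analysis is undefined, because the text does not say whether a 3-df F test or a pooled contrast is meant. The documents do not support going that far. An ANCOVA with treatment as a factor, followed by Tukey's test, is ordinary wording for an omnibus treatment test and then pairs, and Appendix 5 may settle the matter. Requiring a pooled estimate beside an F test could also put a significant test next to an interval that covers zero. This is at most a request for clarification.

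**Conclusion.** The point holds as a minor matter of efficiency. For the three listed comparisons, Tukey's intervals are about 10% wider than Dunnett's and the familywise error is about 2.8% instead of 5%. The width ratio is firm: 1.08 to 1.10 across the near-equal and moderately unequal splits tried, and 1.14 under the strained 3:3:3:1 reading. The power loss, about 9 percentage points at 1.0 SD, rests on an assumed effect and an assumed arm split.

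It applies to the secondary endpoints only. The sentence in SAP 5.5 is worded broadly enough to reach every tested endpoint, but SAP 5.5 and 7.1.4.1 assign the binary primary endpoints a two-sample binomial test. It is also conditional on Appendix 5 planning no dose-versus-dose displays.

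**What to change.** In SAP 5.5, 6.1 and 7.2.4.1, replace Tukey's method with Dunnett's for the three dose-versus-placebo differences, in both the ANCOVA and the repeated-measures analyses, unless Appendix 5 plans dose-versus-dose displays. The change should be made before unblinding.

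It takes a few words in the SAP and a few lines of code. Adjusted dose-versus-dose tests are given up. The full 5% is then used for each endpoint and time point, with the rise in false positives across families shown above, so the exploratory label in SAP 5.4 must stay with the results.

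Optionally, if Appendix 5 does not already do so, 7.2.4.1 could name the test meant by its overall treatment comparison. That choice is the sponsor's.
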